7.4 Bowel Symptom Management Assessment

To obtain data on additional bowel symptom management and assess site standard of care bowel symptom treatment for each participant, sites must complete two questions in the **S1820** Onstudy Form (completed before Step 1 registration), and at each follow-up timepoint (Week 18 and Week 26) using the **S1820** Follow-Up Form.

1 (Week 1)	Introductions, program overview Review food & symptom diary Wellness Plan/goals overview	Food and symptom diary Reflect on wellness plan
2 (Week 2)	Review food and symptom diary Introduction to food trials Introduction to SMART goals	Food and symptom diary Review pages in handbook
3 (Week 3)	Review food and symptom diary Implementation of food trial Set SMART goal	Review handbook as needed Work on SMART goal
4 (Week 4)	Review food and symptom diary Continuation of food trial Set SMART goal	Review handbook as needed Work on SMART goal
5 (Week 5)	Review food and symptom diary Continuation of food trial Other symptom management strategies Set SMART goal	Review handbook as needed Work on SMART goal
6 (Week 6)	Review food and symptom diary Continuation of food trial Other symptom management strategies Set SMART goal	Review handbook as needed Work on SMART goal
7 (Week 8)	Review food trial, problem solving Review survivorship recommendations Set SMART goal	Work on SMART goal **Begin receiving text/email messages
8 (Week 10)	Review food trial, problem solving Review survivorship recommendations Set SMART goal	Review handbook as needed Work on SMART goal **Receive 3 text/email messages this week
9 (Week 14)	Review food trial, problem solving Review survivorship recommendations Set SMART goal	Work on SMART goal **Receive 3 text/email messages this week
10 (Week 18)	Review Wellness Plan Final reflections on knowledge/skills	No further activities **Receive 3 text/email messages this week

7.6 Arm 2: Attention Control Arm

The Attention Control sessions begin within 10 days of randomization and are delivered over approximately 17 weeks via 10 telephone sessions that last about 15-60 minutes each (see [Table 7.6](#)). University of Arizona staff mails a Health Education resource manual to patients; this is used during the sessions to guide discussions between the coach and patients. Our choice of the attention control arm (Healthy Living Education) is based on our previous experience with the design of control conditions for behavioral interventions (i.e. GOG/NRG 225). The 10 topics are selected based on national survivorship guidelines on healthy living post-treatment for cancer survivors.

The Attention Control Arm (Healthy Living Education) is delivered in addition to standard of care for post-treatment rectal cancer survivors. All patients will continue to receive standard care per their physician and care team's direction at the enrollment sites. Our intent is not to replace or change standard care being provided.

The Attention Control sessions are centrally administered via telephone by one trained health coach and one back-up coach (as needed) from the University of Arizona. The health coach will only be working with patients randomized to the Attention Control Arm. The Attention Control Arm coaches are different from the Intervention Arm coaches. The health coach has experience with health coaching among cancer survivors and has been trained on rectal cancer-specific knowledge. They were jointly trained by Drs. [name], [name], and [name]; their delivery of the Health Education program will be monitored by the Study Chair and Co-Chairs throughout the study.

a. Text/Email Messaging

Patients receive electronic communication messaging between scheduled telephone calls after Session 6. Patients have the option of receiving the messages via short smartphone text messaging (SMS) and/or email messaging. The messages are used for retention purposes only. They are standardized messages containing information on the 10 topics listed in [Table 7.6](#). Patients receive three messages per week beginning with Session 6 when calls move to every other week. The messaging will end after Session 10.

b. Newsletters

Patients will receive quarterly newsletters during the 17 weeks of telephone sessions. The newsletters are designed to sustain patient engagement throughout the 17 week intervention. The content will vary each month and will contain information on the ten healthy living education topics designed for the attention control condition.

Table 7.6 Arm 2: Attention Control Call Content

Session	Session Content	Weekly Activities
Session 1 (within 10 days of randomization)	
 • Introductions • Program overview • ACS Diet and Activity 	•
Sessions 2-6 (weekly calls)	
 • Sleep • Skin Care • [name] safety • Active wear • Bone health 	• None
Sessions 7-8 (every other week calls)	
 • Food safety • Survivorship and Surveillance • 	• Receive SMS/emails (3 per week)
Sessions 9-10 (monthly calls)	
 • Evaluating online resources • Clinical Trials • Program Wrap-Up 	• Receive SMS/emails (3 per week)

7.7 Assessment Telephone Calls

- The BFI is administered by telephone by University of Arizona research staff, independent of the study coordinator and study health coaches, during the run-in period, at week 18 and week 26. The questionnaire takes approximately 10 minutes to complete. Data will be collected in REDCap and transferred to RAVE® by University of Arizona staff trained in research data collection.
- 24-hour dietary recalls will be collected during the run-in period, at week 18 and week 26 by trained dietary assessors at the University of Arizona, independent of the study coordinator and study health coaches. The data are collected via telephone and reflect patient recall of all food and beverages consumed in the prior 24-hour period. Data are collected using the University of Minnesota Nutrient Data System for Research (NDS-R); summary nutrient analyses will be derived from the NDS-R nutrient database.

7.8 Criteria for Removal from Protocol Intervention

- Completion of all coaching calls.
- Re-initiation of cancer treatments due to disease recurrence/progression.
- The patient may withdraw from the study at any time for any reason.
- Patient death.

7.9 Discontinuation of Protocol Intervention

- All reasons for discontinuation of study intervention (coaching calls) must be documented in the **S1820** Off Treatment Notice.
- The University of Arizona staff will notify the site via secure email when a patient completes or discontinues the intervention (coaching calls).

7.10 Follow-Up Period

Patients who are registered but ultimately not randomized will require no additional follow up.

All randomized patients will be followed for 26 weeks after randomization.

8.0 TOXICITIES TO BE MONITORED AND DOSE MODIFICATIONS

This is not a treatment study. No dose modification instructions or adverse event information will be collected. Symptoms will be assessed by the investigator at each study visit.

9.0 STUDY CALENDAR

REQUIRED STUDIES	Run-In Reg Step 1	Randomization Reg Step 2	Post-Randomization		
			Weeks 1 – 16 ⁷	Week 18 (+/- 2 weeks)	Week 26 (+/- 2 weeks)
PATIENT QUESTIONNAIRES ⁹					
S1820 Run-In Packet ¹	X				
LARS ⁸	X			X	X
Quality of Life ²	X			X	X
PROMIS Self-Efficacy for Managing Symptoms – Short Form 4a	X			X	X
S1820 Reasons for Managing Bowel Health	X			X	X
Positive and Negative Affect Scale (I-PANAS-SF)	X			X	X
S1820 Baseline Questionnaire ²	X				
Acceptability of Intervention Measure				X	X
SITE COMPLETED FORMS ⁹					
Registration Worksheet - Step 1 (not submitted)	X				
S1820 Patient Contact Form ⁴	X				
Vital Status	X			X	X
S1820 Onstudy	X				
S1820 Investigator Symptom Assessment	X			X	X
S1820 Cover Sheet for Patient-Completed Questionnaires	X			X	X
S1820 Pre-Randomization Off Study	X ⁵				
S1820 Registration Worksheet - Step 2 (not submitted)		X			
S1820 Follow Up				X	X
S1820 Off Treatment Notice ⁶					
SITE COMPLETED ASSESSMENT					
Vital Signs 10	X			X	X
ARIZONA DIRECTED DATA COLLECTION AND PATIENT CONTACTS					
Run-in Telephone Calls	X ³				
Assessment Telephone Calls			X	X ³	X ³
Arm 1: Intervention Telephone Calls			X		
Arm 2: Attention Control Telephone Calls			X		

Footnotes:

- 1 Site must give the patient the run-in packet, but it will not be collected by the site. It is to be completed at home by the patient, for use during run-in telephone calls.
- 2 Use anastomosis or ostomy version, as appropriate
- 3 Includes dietary recalls and BFI assessment (primary endpoint)
- 4 Submitted to Arizona via REDCap
- 5 Submit only if patient will not be registered to Step 2
- 6 Submit after patient completes intervention (coaching calls) or otherwise meets criteria in [Section 7.8](#)
- 7 All coaching calls are planned for completion by Week 18. Due to the patient's schedule, the calls may extend beyond 18 weeks.
- 8 For anastomosis patients only
- 9 All data collection time points (baseline, Week 18, Week 26) should be aligned with standard clinic visits for rectal cancer surveillance (every 3-6 months), per NCCN Clinical Guidelines. If a patient has a clinic visit that falls outside the window for data collection, sites are allowed to collect patient questionnaires by the telephone.
- 10 Vital signs: temperature, weight, heart rate, respiratory rate, and blood pressure. Sites should assess for these signs but are not required to collect the data and submit via Medidata RAVE®.

10.0 CRITERIA FOR EVALUATION AND ENDPOINT ANALYSIS

10.1 Primary Endpoint

The primary endpoint for this study is bowel function at 18 weeks after randomization, as measured by Memorial Sloan-Kettering Cancer Center Bowel Function Instrument (BFI) total score.

The BFI is a validated instrument that assesses bowel function in post-surgery rectal cancer patients. Total scores range from 18 to 90; higher scores indicate better bowel function. The responses are measured on a 5-point Likert scale, apart from the frequency of bowel movements item.^{61, 62} There are separate versions for patients with ostomy (17 items) and anastomosis (20 items). The BFI total score was validated in an observational cohort of post-surgery rectal cancer patients, but only in those with anastomosis not ostomies.⁶¹ The results of a recent confirmatory factor analysis of data from that cohort showed that an eight-item BFI total score that excludes frequency items is valid and reliable and can apply to people with ostomy or anastomosis.⁹² Bowel function is assessed during the run-in (this is the baseline measure), and at Week 18 and Week 26 via telephone interview by the University of Arizona.

10.2 Exploratory Endpoints

a. Bowel function: Dietary, Urgency, Frequency

The BFI has three subscales: a four-item Dietary subscale (score range of 4–20), a four-item Urgency subscale (4–20), and a 6-item Frequency subscale (6–30); higher scores indicate better bowel function. The responses are measured on a 5-point Likert scale, apart from the frequency of bowel movements item.^{61, 62}

b. Low Anterior Resection Syndrome (LARS)

Lower anterior resection syndrome is measured using the LARS Score, a validated 5-item instrument that evaluates severe long-term bowel dysfunction in post-surgery rectal cancer patients.³³ Scores range from 0 to 42 points. Scores are categorized into three groups: no LARS (0-20), minor LARS (21-29), and major LARS (30-42).⁶³⁻⁶⁵ This instrument will only be used with anastomosis patients. LARS is assessed prior to Step 1 registration (baseline), Week 18 and Week 26.

c. Quality of Life

The City of Hope-Quality of Life-Colorectal Cancer (COH-QOL-CRC) is a validated instrument that assesses overall quality of life in post-surgery colorectal cancer patients. It evaluates overall QOL and four QOL dimensions: physical, psychological, social, and spiritual well-being. The overall score is calculated using all subscales, with a range of 0 to 10; higher scores indicate higher quality of life. Subscales scores are also scaled from 0 to 10, with higher scores indicating higher quality of life in that domain.⁶⁶ There are separate versions for patients with ostomy (43 items) and anastomosis (35 items). Quality of life is assessed prior to Step 1 registration (baseline), Week 18 and Week 26.

d. Dietary Quality

Dietary quality is based on the Healthy Eating Index 2015 (HEI-2015), which reflects the American Cancer Society dietary guidance for prevention and

survivorship (greater fruit, vegetable and grain intake, lower animal fat intake, greater fiber intake, and lower empty calorie intake that contributes to undesirable weight status). Dietary quality scores are calculated from the dietary recall data according to the HEI-2015⁶⁷⁻⁷² and adapted for restriction in alcohol intake. Scores range from 0 to 100, with higher scores indicating higher diet quality. Dietary quality is measured during the run-in period (baseline), Week 18 and Week 26.

e. Motivation

Motivation is measured using a 10-item scale assessing motivation to change dietary behaviors in rectal cancer survivors from the **S1820** Reasons for Managing Bowel Health form. It was developed internally, based on the Reasons for Quitting (Intrinsic and Extrinsic Motivation) scale.⁷³ Items are scored on a 5-point Likert scale, from 0 ("Not true at all") to 4 ("Extremely true"). The score is calculated by summing all responses; higher scores indicate higher motivation. Motivation is assessed prior to Step 1 registration (baseline), and at Week 18 and Week 26.

f. Self-Efficacy

Self-efficacy is measured using the Patient-Reported Outcomes Measurement Information System (PROMIS) Self-Efficacy for Managing Symptoms – Short Form 4a, a validated instrument that measures confidence in one's ability to successfully perform specific tasks or behaviors related to self-efficacy for managing symptoms. The four items are scored on a 5-point Likert scale, from 1 ("I am not at all confident") to 5 ("I am very confident"). The overall score is calculated by summing all responses and converting to a PROMIS T-score; higher scores indicate greater self-efficacy.⁷⁴ Self-efficacy is assessed prior to Step 1 registration (baseline), Week 18 and Week 26.

g. Positive and Negative Affect

Affect is measured using the 10-item International Positive and Negative Affect Schedule Short Form (I-PANAS-SF), a validated instrument comprised of two mood scales: Positive Affect (PA) and Negative Affect (NA).^{75, 76} The scores are calculated by summing the responses for positive and negative affect items separately. Scores range from 5 to 25, with higher scores on these scales indicate greater positive affect or negative affect, respectively. Affect is assessed prior to Step 1 registration (baseline), Week 18 and Week 26.

h. Feasibility, adherence, retention, and acceptability

Feasibility, adherence, retention, and acceptability are descriptive measures that will be used to characterize the successfulness of the intervention in this pilot trial and guide the study team in preparing for the Phase III trial. These measures are evaluated based on data obtained throughout the study period.

Feasibility is measured by the percentage of patients who successfully complete ("pass") the run-in period and are randomized. Successful completion is defined as meeting all five of the following measures:

1. Patient answers the telephone calls from trained staff at the University of Arizona.
2. Patient completes 24-hour dietary recall with trained staff from University of Arizona.

3. Patient completes the food and symptom diary with least 3 entries of any kind (food OR symptom) for 3 days (consecutive or not).
4. Patient returns their food and symptom diary, by mail or email, to the University of Arizona within 14 days of completion.
5. Patient completes the BFI with trained staff from University of Arizona.

Adherence measures successful completion of intervention or attention control coaching calls. Adherence is defined as completing all five of Sessions #1-5 and at least three of Sessions #6-10 within 18 weeks after randomization; patients who do not meet this criterion are classified as non-adherent.

Retention is defined by completion of follow-up assessments in Step 2, including those administered at follow-up site visits and the dietary recalls.

Acceptability is measured for all participants using the Acceptability of Intervention measure (AIM)⁷⁷. It is scored on a 5-point Likert scale from 1 ("completely disagree") to 5 ("completely agree"). Acceptability is assessed at Week 18 and Week 26.

11.0 STATISTICAL CONSIDERATIONS

11.1 Primary Endpoint and Sample Size

The primary endpoint for this study is bowel function total score at 18 weeks after randomization, as measured by the BFI. Thirty-seven patients per arm (74 total) will provide 80% power to detect an effect size of 0.5, based on a two-sample t-test with a 1-sided alpha=0.1. The effect size is justified by data from a study of post-surgery rectal cancer patients with anastomosis, which gave a BFI SD estimate of 9.3 points^{61, 62, 78}, and a clinically meaningful study arm difference of approximately 4.6 points as defined by the Sloan empirical rule effect size (defined as a mean difference of approximately 8% of BFI range).⁷⁹ We assume that the 0.5 SD effect size is similarly meaningful for the validated eight-item BFI total score.⁹² We will accrue additional patients to account for 7% ineligibility and 15% attrition at 6 months, for a total accrual goal of 94 randomized patients.

11.2 Primary Endpoint Analyses

The analysis of the primary endpoint will be conducted in all eligible patients randomized to the study with 18-week BFI data regardless of adherence to the coaching calls, according to a modified intention-to-treat principle. Study arm differences in BFI at 18 weeks will be assessed by a linear regression model as a function of randomization assignment, BFI baseline value, and stratification factors. Due to the low safety risks of this study, we will not perform an interim futility analysis.

11.3 Other Analyses

Given the modest size of this trial, the exploratory endpoint analyses are considered hypothesis-generating. Study arm differences in BFI at 26 weeks will be assessed by a linear regression model as a function of randomization assignment, BFI baseline value, and stratification factors. Other continuous exploratory outcomes at both 18 and 26 weeks (BFI subscales, LARS, quality of life, dietary quality, motivation, self-efficacy, and positive/negative affect) will be assessed by a repeated measures linear regression model as a function of

randomization assignment, baseline value of the outcome, stratification factors, and visit. Robust standard errors will be estimated via generalized estimating equations to adjust for correlation between repeated outcome measures. The dependent variables will be transformed to approximate normality as appropriate.

Accrual rates and feasibility will be summarized. Study arm differences in adherence and retention will be assessed by chi square tests. Study program acceptability will be compared across arms via t-test.

Although the sample size provides limited statistical power for subgroup analyses, we will explore the impact of sex by reanalyzing all outcomes according to sex as feasible. The potential for differential intervention effects according to sex on the primary endpoint will also be considered.

To assess the sensitivity of intervention effects to the potential confounding factor of site-based symptom management, additional exploratory BFI models will adjust for such treatments used by participants at baseline and during the intervention.

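### The separate Week 26 regression for the BFI total ignores Week 18 scores; a two-visit likelihood model would guard objective 1.2a against dropout that differs by arm

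*Combined protocol and SAP*

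**What the plan says.** Section 11.2 fits the primary Week 18 comparison by linear regression on arm, baseline BFI and stratification factors, in "all eligible patients randomized to the study with 18-week BFI data". That restriction to observed scores is explicit.

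For Week 26, Section 11.3 says: "Study arm differences in BFI at 26 weeks will be assessed by a linear regression model", with the same terms. It does not define the analysis set in words. Neither section describes imputation, a joint model for the BFI total or a missing-data sensitivity analysis, so restriction to patients with a Week 26 score is an inference from the model.

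The other continuous outcomes, including the BFI subscales, "will be assessed by a repeated measures linear regression model as a function of" arm, baseline value, stratification factors and visit, with robust standard errors from generalized estimating equations (GEE). No arm-by-visit term and no working correlation are listed.

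Section 11.1 allows for "15% attrition at 6 months" and does not split the loss between the periods before and after Week 18. Section 11.3 labels all exploratory analyses hypothesis-generating.

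**The concern.** Objective 1.2a compares the arms on the BFI total at 26 weeks, about two months after coaching is planned to end. A patient who gives a Week 18 score and then stops contributes nothing to that comparison, although the Week 18 score is informative about the missing one.

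Suppose poor Week 18 scorers stop more readily in the intervention arm and not in the control arm. The intervention patients who remain are then a favourable selection, and the Week 26 difference overstates a lasting benefit. The reverse pattern understates it. The planned chi-square test of retention compares the proportions retained. It cannot show that the two arms lost the same share but different kinds of patient.

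Section 10.2h describes the trial as a pilot that prepares for a Phase III trial, so a picture of durability that is too good or too poor would carry forward.

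**Working it through.** **1. The plan's own figures.** Section 11.1: "Thirty-seven patients per arm (74 total) will provide 80% power to detect an effect size of 0.5". The test compares two means by t-test, one-sided at the 10% level. Normal approximation: n per arm = 2(1.2816 + 0.8416)² / 0.5² = 2 × 4.508 / 0.25 = 36.06, so 37. The noncentral t gives power 0.804 at 37 per arm and 0.796 at 36. The effect size follows from 4.6 / 9.3 = 0.495. Inflation: 74 / (0.93 × 0.85) = 93.6, so 94. All figures reproduce.

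**2. How many patients are involved.** Eligible: 94 × 0.93 = 87.4, about 87. With a Week 26 score: 87 × 0.85 = 74. So at most about 13 patients could have a Week 18 score that goes unused. If 7% are already missing at Week 18 (an assumption), the number is 87 × (0.15 − 0.07), about 7.

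**3. What drives the bias.** Given baseline, the slope of the Week 26 score on the Week 18 score is (r_v − r_b²) / (1 − r_b²), where r_b is the baseline correlation and r_v the between-visit correlation. The bias is approximately this slope times the between-arm difference in how far dropout shifts the completers' mean Week 18 residual. With r_b = 0.5:
- r_v = 0.6: (0.6 − 0.25) / 0.75 = 0.47
- r_v = 0.7: (0.7 − 0.25) / 0.75 = 0.60
- r_v = 0.8: (0.8 − 0.25) / 0.75 = 0.73

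If dropout shifts both arms alike, the difference is zero and so is the bias.

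**4. Simulation, dependence in the intervention arm only.** Assumed, because the documents do not give them: 7% missing at Week 18 and 15% at Week 26 in both arms, r_b = 0.5, no true effect, and lower Week 18 scores raising intervention-arm dropout. n = 87, 8,000 trials per setting.

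| Log-odds of dropout per SD | Bias, r_v = 0.6 | Bias, r_v = 0.8 |
|---|---|---|
| 0.7 | 0.021 SD | 0.035 SD |
| 1.1 | 0.034 SD | 0.054 SD |
| 1.6 | 0.043 SD | 0.069 SD |

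In points at SD 9.3: 0.021 × 9.3 = 0.20 to 0.069 × 9.3 = 0.64. The column ratios (1.67, 1.59, 1.60) agree well with 0.73 / 0.47, about 1.57, from step 3. Repeat runs gave 0.02 to 0.06 SD. A one-sided 10% test would reject in 12.2% to 18.0% of trials, but Section 11.3 sets no alpha for Week 26, so that is an illustration only. The joint likelihood model's bias was at most 0.001 SD here and within 0.004 SD on repeat.

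**5. Other mechanisms** (n = 87, SD 9.3, r_b = 0.5, r_v = 0.7 unless noted; bias in BFI points).

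| Dropout between visits | Separate regression | Joint likelihood model |
|---|---|---|
| Unrelated to score | about 0 | about 0 |
| Week 18 score, opposite directions by arm | 1.18 (1.44 at r_v = 0.8) | about 0 |
| Unseen Week 26 score, one arm | 0.87 | 0.57 |
| Unseen Week 26 score, opposite directions | 1.97 | 1.29 |

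When dropout depends equally on the Week 18 score in both arms, the separate regression's bias under no true effect was −0.006 to +0.002 SD. With a true effect it ranged from 0 to −0.14 points.

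**6. Precision.** SD of the Week 26 estimate, separate versus joint: 1.71 and 1.71 points with no dropout; 1.84 and 1.81 with 10% random dropout.

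**7. Would the listed GEE model serve?** It has no arm-by-visit term, so it estimates one effect pooled over both visits. If the true effect falls from 4.65 points at Week 18 to 2.3 at Week 26, it misses the Week 26 value by about 1.2 to 1.4 points; if the effect falls to 0, by about 2.6. Adding arm-by-visit under an independence working correlation leaves the dropout bias in place (0.31 against 0.32 points for the separate regression).

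**Limits.** Sex and ostomy status were left out of the points-scale runs in steps 5 to 7. The 9.3-point SD comes from patients with anastomosis, and Section 11.1 only assumes that the effect size carries over to the eight-item total, so the SD-unit results are the safer guide.

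**The case against.** The case for leaving the plan alone is substantial.

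- The bias needs score-dependent dropout that differs by arm, and the documents give no evidence of it. Programme contact is planned to end by about Week 18 in both arms (Sections 7.5, 7.6 and 9.0), although calls may run later. The BFI is collected centrally by telephone, independently of the coaches and by a blinded assessor (Sections 7.7 and 18.4). Stopping coaching does not itself end BFI collection.
- The effect is small. In the one-arm setting the root mean squared error was 0.204 to 0.210 SD for the separate regression and 0.197 to 0.203 for the joint model.
- The endpoint is exploratory, and a separate regression does deliver a contrast specific to Week 26.

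All of this stands and limits the weight of the point. None of it shows the separate regression to be as good as the joint model, which uses more of the data and was no less precise.

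Four stronger readings are tempting, and none is supported:

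- *Any dropout related to the Week 18 score biases the result.* With no true effect and equal dependence in both arms, the bias is about zero.
- *The primary result is at risk.* Losses after Week 18 do not touch the Section 11.2 test or the sample size. A joint model narrows the Week 18 standard error by only 1 to 2% when some patients miss Week 18 and return, and not at all under monotone dropout.
- *The model for the other outcomes is the better standard.* As listed, it pools the visits and would not answer objective 1.2a.
- *A joint model cures missing data at no cost.* It removes the bias only when dropout is explained by observed data, and it needs a modelled covariance.

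**Conclusion.** The point holds as an inexpensive improvement to an exploratory analysis. The Week 26 BFI regression leaves unused the Week 18 scores of up to about 13 patients, about 7 under the assumed split. If loss between visits depends on those scores differently by arm, the contrast is biased by about 0.02 to 0.07 SD under one-arm dependence, and by 1.2 to 1.4 points (0.13 to 0.15 SD) in the extreme case of opposite dependence. Section 11.1 takes as its yardstick a "clinically meaningful study arm difference of approximately 4.6 points". These sizes rest on assumed correlations, dropout timing and dropout mechanisms, none of which the documents give. A joint likelihood model removes the bias when dropout is explained by observed data and otherwise only reduces it.

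**What to change.** Leave the Section 11.2 Week 18 regression as the primary test. In Section 11.3, replace the sentence on the Week 26 BFI total with the following:

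- **Model.** One likelihood-based repeated-measures model of the BFI total at Weeks 18 and 26, with arm, visit, arm × visit, baseline BFI, baseline × visit, sex and ostomy status, and an unstructured covariance for the two visits.
- **Analysis set.** All eligible randomised patients with at least one post-baseline BFI.
- **Reporting.** Take the Week 26 contrast from this model for objective 1.2a. Show its Week 18 contrast beside the primary result and label it as supportive.
- **Sensitivity analysis.** Impute missing Week 26 scores from the model, then shift the imputed values by a stated range in one arm at a time. For scale, a 4.6-point shift in an arm with 15% missing moves the contrast by 0.15 × 4.6 = 0.69 points.

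Do not simply add the BFI total to the GEE model as listed.

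The cost is a paragraph of SAP text and one standard model on data already collected. The downsides are a modelled covariance and a second Week 18 estimate to report. Sample size, alpha and the primary analysis do not change.

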
This study was designed to include women and minorities. We expect adequate representation of women in the trial. The anticipated accrual in the ethnicity/race and sex categories for randomized patients is shown in the table below.

Racial Categories	Ethnic Categories				Total	
	Not Hispanic or Latino		Hispanic or Latino			
	Female	Male	Female	Male		
American Indian/ Alaska Native	0	0	0	0	0	
Asian	2	1	0	0	3	
Native Hawaiian or Other Pacific Islander	0	0	0	0	0	
Black or African American	4	2	0	0	6	
White	50	31	2	1	84	
More Than One Race	0	1	0	0	1	
Total	56	35	2	1	94	

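### The GEE robust standard errors in Section 11.3 carry no small-sample correction; under the default they run about 7-10% small in the analyses of men (minor)

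*Combined protocol and SAP*

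**What the plan says.** Section 11.3 (Other Analyses) fits a repeated measures linear regression to the continuous exploratory outcomes at Weeks 18 and 26. The model terms are "randomization assignment, baseline value of the outcome, stratification factors, and visit". On the standard errors it says only: "Robust standard errors will be estimated via generalized estimating equations to adjust for correlation between repeated outcome measures". No small-sample correction, degrees of freedom or reference distribution is given, and none is ruled out.

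The same section commits to "reanalyzing all outcomes according to sex as feasible", while conceding that power for subgroups is limited and calling the exploratory analyses hypothesis-generating.

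The 26-week BFI total (Section 11.3) and the primary 18-week BFI total (Section 11.2) use linear regression with one observation per patient. Feasibility is summarised descriptively, adherence and retention are compared by chi-square test, and acceptability by t-test. The GEE sentence covers none of these.

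**The concern.** The ordinary sandwich estimator uses fitted residuals in place of the true errors. Fitted residuals are smaller on average, because the model has been drawn towards the data. The shortfall grows as the number of patients falls relative to the number of patient-level parameters. A normal reference adds to it by ignoring the uncertainty in the standard error itself. Both push the same way: intervals too narrow and p-values too small.

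With several hundred patients this would not matter. Here the full sample is about 74, and the planned analyses by sex divide it further. LARS is smaller again, because only anastomosis patients complete it. The distortion is also unequal: larger in men than in women, so the two sets of intervals would not be equally reliable when read side by side. Objective 1.2f asks how exploratory outcomes vary by sex, and the rationale in Section 2.0 foresees tailoring the intervention on sex-specific data. Intervals should therefore have about the coverage they claim.

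**Working it through.** **1. The plan's own figure.** Section 11.1 tests at the one-sided 10% level with a t-test and states: "Thirty-seven patients per arm (74 total) will provide 80% power to detect an effect size of 0.5". The two-sample formula gives 37 per arm, and the noncentral t distribution gives 80.4% power at 37 per arm. Inflating for "7% ineligibility and 15% attrition at 6 months, for a total accrual goal of 94 randomized patients": 74 / (0.93 × 0.85) = 74 / 0.7905 = 93.6, so 94. The plan's sample size is reproduced.

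**2. Patients by sex.** Section 2.0 states: "The anticipated accrual in the ethnicity/race and sex categories for randomized patients is shown in the table below". Its Total row gives 35 + 1 = 36 men and 56 + 2 = 58 women. Applying the same allowances to each sex:
- Men: 36 × 0.7905 = 28.5, about 28.
- Women: 58 × 0.7905 = 45.8, about 46.
- LARS in men: the documents give no anastomosis share by sex, so about 20 is an assumption.

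**3. A hand check.** Let n be the number of patients and k the number of patient-level parameters. The average shortfall in the variance is roughly k/n, so the standard error is roughly √(1 − k/n) of its true value. If the statistic divided by that shortfall follows a t distribution on n − k degrees of freedom, the error at a nominal 5% is P(|t| > 1.96 × √(1 − k/n)).

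| Analysis | n | k | √(1 − k/n) | Approximate error |
|---|---|---|---|---|
| All (intercept, arm, baseline, sex, ostomy status) | 74 | 5 | 0.966 | 6.3% |
| Women (sex drops out) | 46 | 4 | 0.956 | 6.8% |
| Men | 28 | 4 | 0.926 | 8.2% |
| LARS in men (ostomy status also drops out) | 20 | 3 | 0.922 | 8.9% |

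This needs no assumed correlation, but it uses average leverage, so it is only a guide.

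**4. Simulation under no treatment effect.** 20,000 replicates per setting of the planned model: two complete visits, Gaussian errors, 1:1 arms, working independence. Assumptions not in the documents: residual within-patient correlation 0.4-0.7, baseline correlation 0.5, ostomy share 10-40%. Monte Carlo error is about 0.2 points. The last column adds further runs of the same model with fewer replicates and somewhat different assumptions (for example, both correlations 0.6, or some Week 26 values missing).

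| n | Mean SE / true SD | Error at nominal 5%, uncorrected, normal reference | Further runs |
|---|---|---|---|
| 74 | 0.96-0.97 | 6.1-6.4% | 6.1-6.5% |
| 46 | 0.94-0.96 | 6.8-7.0% | 6.9-7.2% |
| 28 | 0.91-0.93 | 8.1-8.5% | 8.0-9.2% |
| 20 | 0.91 | 8.7% | 9.0-9.6% |

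In men a nominal 95% interval then covers about 91.5-92%. The further runs put the standard errors in men 8-10% short. At a nominal two-sided 20%, which matches the one-sided 10% of the primary test, rejection is 21.7-22.2% at n = 74 and 24.3-25.0% at n = 28.

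**5. Candidate corrections, same simulation.**
- t reference alone, standard error uncorrected: 6.7-7.1% in men, so not enough.
- Kauermann-Carroll with t on n − k degrees of freedom: 5.0% at 74, 4.9-5.1% at 46, 4.9-5.2% at 28 and 5.0% at 20. Further runs gave 4.7-5.7%.
- Mancl-DeRouen with t: 3.5-3.7% at 28 and 3.4% at 20, so it over-corrects.

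**The case against.** The strongest reply is that the plan is silent rather than wrong. It does not say that the standard errors will be uncorrected, and an analyst could apply a correction without departing from it. That stands: the defect is an unspecified choice whose usual default is too narrow. A reader might call the method wrong as written; the text does not support that.

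A second reply is that little depends on it. A reader might infer that false sex differences would drive the tailoring of the intervention. The only differential-effect question in Objective 1.2f and Section 11.3 concerns the primary endpoint, which is analysed by ordinary linear regression. What remains is sex-specific estimates on secondary scales, planned only where feasible, with no significance threshold set for them. This also stands, and it limits the severity. It does not remove the point, because a hypothesis-generating interval should still have about its stated coverage.

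A third reply concerns size. Simulating 28 men and then deleting another 10% at Week 26 has given 9.7%, and 11% with 20 patients. The 15% attrition in Section 11.1 is already at 6 months, which is Week 26, so those settings partly count attrition twice. If every patient lost by then still supplied Week 18 data, about 36 × 0.93 = 33 men would contribute, with 15% missing at Week 26. Runs in that setting give about 8-9%. The documents do not support figures of 10% or more for men.

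Finally, a reader might argue that GEE should give way to a mixed model because of missing data. Unweighted GEE remains consistent if missingness depends only on covariates in a correctly specified mean model. No bias from missing data was calculated here and the mixed model was not simulated, so this check gives no ground for replacing GEE.

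**Conclusion.** The point holds and is minor. If the sentence is carried out with the ordinary sandwich and a normal reference, standard errors are about 7-10% too small in men and the two-sided error is about 8-9% at a nominal 5%. The error is about 7% in women and about 6-6.5% overall. For LARS in men it is about 9-10% if about 20 have an anastomosis.

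The direction follows from the estimator, and the hand check agrees with the simulated size. The exact figures rest on the assumed correlations, ostomy share and Gaussian errors. Skewed scores and the planned transformations were not simulated and could move them. The primary analysis, the 26-week BFI total, the sex-by-arm question on the primary endpoint, the chi-square tests and the acceptability t-test are unaffected, so no confirmatory conclusion is at risk.

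**What to change.** Amend the sentence in Section 11.3 to say that the GEE robust standard errors will use a small-sample bias correction (for example Kauermann-Carroll) with a t reference distribution, with degrees of freedom equal to patients minus patient-level parameters, in both the overall and the sex-specific analyses. For 28 men that is 28 − 4 = 24 degrees of freedom; for the full sample it is 74 − 5 = 69.

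The cost is one sentence and a software setting; the data collected and the sample size do not change. Intervals widen by roughly the ratio of critical values divided by √(1 − k/n). Overall that is (1.995 / 1.960) / 0.966 = 1.05, about 5%. In men it is (2.064 / 1.960) / 0.926 = 1.14, about 14%. That widening is what brings the error back to about 5%.
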